After all Screen/Baseline assessments are complete subjects may be randomized.

Subjects in the combination arm may receive the first infusion of Gamunex-C on Screen/Baseline and Randomized Treatment visit (Day 1) if eligibility criteria are met, and all pre-infusion assessments are performed. Subjects in the combination arm will receive a total of 2 g/kg Gamunex-C in divided doses. At the prerogative of the Principal Investigator the 2 g/kg dose may be divided into 4 days (500 mg/kg/day) or 5 consecutive days (400 mg/kg/day).

Vital signs will be monitored during Gamunex-C infusion. Vital signs will be measured within 1 hour prior to the start of Gamunex-C infusion, 30 minutes after the start of infusion, and hourly through the end of Gamunex-C infusion. If the systolic blood pressure measured within 1 hour prior to the start of Gamunex-C infusion is > 160 mm Hg, then measures to lower blood pressure below this threshold should be administered and documented prior to commencing Gamunex-C infusion. To commence the Gamunex-C infusion, the systolic blood pressure must be < 160 mm Hg.

7.2.3 SMT, Randomized IVIG Treatment, Daily Evaluations (Days 2 through 10 inclusive) and Additional Day 5±1 Day Assessments

All subjects receive continued SMT. Subjects randomized to IVIG plus SMT will receive the remainder of the net 2 g/kg dose in divided doses at the Principal Investigator's prerogative on consecutive days through Day 4 (500 mg/kg/day) or through Day 5 (400 mg/kg/day) to achieve the total dose of 2 g/kg body weight. Subjects receiving Gamunex-C infusions will have vital signs measured within 1 hour prior to the start of each Gamunex-C infusion, 30 minutes after the start of infusion, and hourly through the end of Gamunex-C infusion. If the systolic blood pressure measured within 1 hour prior to the start of Gamunex-C infusion is > 160 mm Hg, then measures to lower blood pressure below this threshold should be administered and documented prior to commencing Gamunex-C infusion. To commence the Gamunex-C infusion, the systolic blood pressure must be < 160 mm Hg.

Daily assessments include the following:

- Ordinal Scale assessment
- NEWS ([Appendix 2](#))
- Clinical features key symptoms: fever, cough, shortness of breath, fatigue, myalgia etc.
- Vital signs (temperature, systolic and diastolic blood pressure, pulse, respiratory rate)
- Record any supplemental oxygen administration (type, %, flow start/end date/time)

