- Record details of mechanical ventilation parameters (start/end date/time)
- Record oxygen saturation (specify on or off oxygen supplementation)
- Record daily 24-hour fluid balance (intake and output) while in hospital
- Record body weight for assessing fluid balance twice daily on Days 1 through 5 inclusive (at least 8 hours should separate the time from the first recorded weight)

GRIFOLS Bioscience Industrial Group	Number	BLG-CL-PRT-000020	Version	4.0	Status	Effective	Effective Date	19-Jul-2021	Page	51 of 91
	GC2007 - A Multicenter, Randomized, Open-label Parallel Group Pilot Study to Evaluate Safety and Efficacy of High Dose Intravenous Immune Globulin (IVIG) plus Standard Medical Treatment (SMT) versus SMT alone in									

- Record SAEs and TEAEs
- Record standard care concomitant medications

All laboratory tests and serum and plasma samples are required for all study subjects, regardless of treatment assignment. For subjects randomized to IVIG plus SMT all laboratory samples must be obtained prior to the Gamunex-C infusion on the designated day.

On Day 5 ± 1 day the following *additional* assessments will be performed:

- Assessment of ARDS (Berlin Criteria) ([Appendix 3](#))
- SOFA score ([Appendix 4](#))
- Respiratory sample for quantitative measurement of SARS-CoV-2 viral load by NAT or PCR (real-time RT-PCR) (obtained via nasopharyngeal swab)
- Sample for quantitative measurement of IgM and IgG antibodies to SARS-CoV-2 (store serum samples frozen at -70°C for later analysis at an external lab)
- Serum Chemistry (creatinine, albumin, ALT, total bilirubin, LDH)
- Ferritin (serum), D-dimer (plasma, sodium citrate tube), CRP (serum)
- Hematology: absolute lymphocyte count and standard hematology (hemoglobin, hematocrit, platelet count, leukocyte count with differential)
- DAT
- Cytokine panel (IL-1 β , IL-10, IL-6, IL-8, IL-2, interferon γ , and TNF- α). Note: serum samples must be stored at -70°C for later analysis at a reference laboratory.

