Appendix 1 Schedule of Study Procedures

Study Period	Screen/ Baseline	1 st IP	SMT and Daily Evaluations										Follow- Up	Follow-Up Clinic Visit Day			Phone Checks	
			2	3	4	5±1 day	6	7	8	9	10	11-14 Daily if in hospital		15±1 e day	16-28 Daily if in hospital	29 ^{e,f} ± 1 day	Day 60 ± 2 days	Day 90 ± 2 days
Study Day	1																	
Procedures/assessments																		
Informed consent	X																	
Inclusion/exclusion criteria	X																	
Demography (age [year of birth], age at screening [years], gender [if female, fertility status], race, and ethnicity), disease characteristics (date of exposure, date of onset ^a)	X																	
Pregnancy test ^b	X																	
Ordinal Scale (at the 1st assessment of a given day) ^c	X		X	X	X	X	X	X	X	X	X	X	X	X	X	X	X	
National Early Warning Score (NEWS) Appendix 2	X		X	X	X	X	X	X	X	X	X	X	X	X	X	X	X	
Clinical features key symptoms: fever, cough, shortness of breath, fatigue, myalgia etc.	X		X	X	X	X	X	X	X	X	X	X	X	X	X	X	X	
Vital signs (temperature, systolic and diastolic blood pressure, pulse, respiratory rate)	X	X ^k	X ^k	X ^k	X ^k	X ^k	X ^k	X	X	X	X	X	X	X	X	X	X	
Initial Body Weight for determining all IVIG doses if randomized to combination arm	X																	
Body weight for assessing fluid balance twice daily (at least 8 hours)		X	X	X	X	X	X											

Study Period	Screen/ Baseline	1 st IP	SMT and Daily Evaluations										Follow- Up	Follow-Up Clinic Visit Day			Phone Checks	
			2	3	4	5±1 day	6	7	8	9	10	11-14 Daily if in hospital		15±1 e day	16-28 Daily if in hospital	29 ^{e,f} ± 1 day	Day 60 ± 2 days	Day 90 ± 2 days
Study Day	1																	
Procedures/assessments																		
should separate the time from the first recorded weight)																		
Record result of historical SARS-CoV-2 PCR (qualitative RT-PCR) or other FDA-approved or regulatory-authority-approved diagnostic assay in any specimen during the current hospital admission prior to randomization (eligibility criterion)	X																	
Record any supplemental oxygen administration (type, %, flow start/end date/time)	X		X	X	X	X	X	X	X	X	X	X	X	X	X	X	X	
Record any mechanical ventilation (start/end date/time)	X		X	X	X	X	X	X	X	X	X	X	X	X	X	X	X	
Record oxygen saturation (specify on or off oxygen supplementation)	X		X	X	X	X	X	X	X	X	X	X	X	X	X	X	X	
Randomization (after all Screen/Baseline assessments complete)	X																	

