#### **4.4 Handling of Dropouts or Missing Data**

Missing data will be treated as missing and no method for imputation is planned for study population or safety analyses except for the partial end dates/times for concomitant medications (Section 5.6) and partial onset dates/times for AEs (Section 7.2.1). When applicable, missing data for binary and selected continuous efficacy endpoints will be imputed using a most conservative/worst case approach, and the related details are described in Section 6.

Time to event endpoints will have events coded as right censored or competing events per the

following table:

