### **Duration of ICU stay (Actual and Medical Equivalence)**

The duration (number of days) of ICU stay from post-randomization through Day 29 will be calculated based on ICU admission and discharge (actual and medical equivalence) dates recorded on the eCRF. Number of days in the ICU will be compared between treatment groups using an ANOVA model, including number of days in the ICU as a dependent variable and treatment group as a fixed effect. From this model, the LS means and 95% CIs for each treatment group, the treatment difference in the LS means, the 95% CI for the difference, and the associated p-value will be presented. If appropriate, an ANCOVA model may instead be used to additionally adjust for baseline characteristics such as age and gender.

Subjects who died while in the ICU will be assigned as in the ICU for the number of days remaining from the day of death to Day 29 for the analysis. Subjects who were at ICU at study completion will be assigned an ICU end date equals to the date of completion for the purpose of deriving the number of ICU days.

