### **Duration of mechanical ventilation**

The duration (number of days) on mechanical ventilation from post randomization through Day 29 will be calculated based on the start/stop dates of mechanical ventilation recorded on the eCRF All Visits page “General Duration of Hospitalization, & Overall Requirement for Mechanical Ventilation, ICU Admission and/or Oxygen Supplementation”. Number of days on mechanical ventilation will be compared between treatment groups using an ANOVA model, including number of days on mechanical ventilation as a dependent variable and treatment group as a fixed effect. From this model, the LS means and 95% CIs for each treatment group, the treatment difference in the LS means, the 95% CI for the difference, and the associated p-value will be presented. If appropriate, an ANCOVA model may instead be used to additionally adjust for baseline characteristics such as age and gender.

Subjects who died during the hospitalization without a stop date of mechanical ventilation recorded on the eCRF will be assigned as being on mechanical ventilation for the number of days remaining to Day 29 for the analysis. Subjects who had mechanical ventilation ongoing at study completion will be assigned a mechanical ventilation end date equals to the date of completion for the purpose of deriving duration of mechanical ventilation. Subjects who are never placed on mechanical ventilation through Day 29 will be included in the analysis with a value of zero days on mechanical ventilation.

A listing of all mechanical ventilation and oxygen administration data collected throughout the study will be provided.

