### **Duration of Hospitalization (Actual and Medical Equivalence)**

The duration (number of days) of hospitalization from post-randomization through Day 29 will be calculated based on hospital admission and discharge (actual and medical equivalence) dates recorded on the eCRF. Number of days in the hospital will be compared between treatment groups using an ANOVA model, including number of days in the hospital as a dependent variable and treatment group as a fixed effect. From this model, the LS means and 95% CIs for each treatment group, the treatment difference in the LS means, the 95% CI for the difference, and the associated p-value will be presented. If appropriate, an ANCOVA model may instead be used to additionally adjust for baseline characteristics such as age and gender.

Subjects who died while in the hospital will be assigned as in the hospital for the number of days remaining from the day of death to Day 29 for the analysis. Subjects who were in the hospital at study completion will be assigned a hospitalization end date equals to the date of completion for the purpose of deriving the duration of hospitalization.

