### **Duration of any oxygen use**

The duration (number of Days) of any oxygen use from Day 1 through Day 29 will be calculated based on the start/stop date of using oxygen supplementation recorded on the eCRF All Visits page "General Duration of Hospitalization, & Overall Requirement for Mechanical Ventilation, ICU Admission and/or Oxygen Supplementation". Number of days on oxygen will be compared between treatment groups using an analysis of variance (ANOVA) model, including number of days on oxygen as a dependent variable and treatment group as a fixed effect. From this model, the LS means and 95% CIs for each treatment group, the treatment difference in the LS means, the 95% CI for the difference, and the associated p-value will be presented. If appropriate, an analysis of covariance (ANCOVA) model may instead be used to additionally adjust for baseline characteristics such as age and gender.

Subjects who died during the hospitalization without a stop date of using oxygen supplementation recorded on the eCRF will be assigned as being on oxygen for the number of days remaining to Day 29 for the analysis. Subjects who had oxygen use ongoing at study completion will be assigned an oxygen use end date equals to the date of completion for the purpose of deriving duration of oxygen use. Subjects who never received supplemental oxygen through Day 29 will be included in the analysis with a value of zero days of oxygen use.

A listing of all supplemental oxygen and saturation ( $SpO_2$  and  $SaO_2$ ) data collected throughout the study will be provided.

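### Ventilation and oxygen days extend a death to Day 29 only when no stop date is recorded, so a death on support can score as short support if the date of death is entered as the stop date

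*SAP*

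**What the plan says.** SAP 6.2 has four duration endpoints that run to Day 29 and are compared by ANOVA on the number of days. They treat death in two different ways.

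- ICU days: "Subjects who died while in the ICU will be assigned as in the ICU for the number of days remaining" up to Day 29. Death in the ICU is the only trigger.
- Hospital days: "Subjects who died while in the hospital will be assigned as in the hospital for the number of days remaining" up to Day 29. Death in hospital is the only trigger.
- Ventilation days: "Subjects who died during the hospitalization without a stop date of mechanical ventilation recorded on the eCRF will be assigned as being on mechanical ventilation" over the days left to Day 29. There are two triggers, death in hospital and an empty stop-date field.
- Oxygen days: "Subjects who died during the hospitalization without a stop date of using oxygen supplementation recorded on the eCRF will be assigned as being on oxygen" over the days left to Day 29. The same two triggers apply.

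In every other case, ventilation and oxygen days come from the recorded start and stop dates. SAP 4.6 counts a duration as end date minus start date plus 1. Both subsections also give zero days to subjects who never had the support in question.

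The protocol has sites collect end dates and times. Section 7.2.3 asks for "Record any supplemental oxygen administration (type, %, flow start/end date/time") and "Record details of mechanical ventilation parameters (start/end date/time"), and Appendix 1 has the row "Record any mechanical ventilation (start/end date/time"). Neither document says what to enter as the end date when a subject dies on support, or that a stop date equal to the date of death is to be disregarded.

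**The concern.** A stop date can mean two things: support ended while the subject was alive, or the subject died on support and the site closed the record with the date of death. The SAP rule reads both as the first. Two subjects with the same course, both dying on the ventilator on Day 10, can then score 29 days and 10 days because one field was filled in differently.

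The error has a direction. Extending a death to Day 29 keeps an early death from looking like a short, favourable course. Where a stop date is entered at death, that protection is lost, and the arm with more deaths loses more of its days. A difference in mean days that reflects mortality is then understated. The protocol enrols subjects who need ventilation and/or supplemental oxygen (inclusion criterion 3b), so death on support is the very case the rule has to handle.

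There is also a small gap in wording. Read literally, a subject who dies in hospital without ever having been ventilated has no stop date and so meets the death rule as well as the zero rule. Zero is the sensible reading, and one clause would settle it.

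**Working it through.** The plan gives no figure on this point, so there is none to reproduce. The check applies the SAP's own formula to the two possible entries.

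**Inputs from the documents.** Duration = end − start + 1 (SAP 4.6). The horizon is Day 29 (SAP 6.2). About 100 subjects are randomised 1:1 (SAP 3.1 and 9), so n = 50 per arm. The ANOVA has treatment as its only effect, so the estimate is a difference in arm means.

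**Assumed, because the documents do not give them.** Day of death t; share f of deaths on support with the date of death entered as stop date; excess D of deaths on support in one arm; survivors' days.

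**Step 1: one subject on support from Day 1 who dies on support on Day t.** With a blank stop date the score is 29 − 1 + 1 = 29. With the date of death entered it is t − 1 + 1 = t. The loss is 29 − t.

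| Day of death | Stop date blank | Date of death entered | Loss | Fall in arm mean, loss/50 |
|---|---|---|---|---|
| 4 | 29 | 4 | 25 | 0.50 |
| 10 | 29 | 10 | 19 | 0.38 |
| 20 | 29 | 20 | 9 | 0.18 |

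**Step 2: difference between arms, with t and f the same in both.** An arm with d deaths on support has its mean lowered by f × d × (29 − t)/50. Survivors' days do not change, so they cancel. The difference shrinks by f × D × (29 − t)/50.

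| D | t | f = 25% | f = 50% | f = 100% |
|---|---|---|---|---|
| 4 | 10 | 0.38 | 0.76 | 1.52 |
| 8 | 10 | 0.76 | 1.52 | 3.04 |
| 8 | 20 | 0.36 | 0.72 | 1.44 |

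For example, 0.5 × 8 × 19/50 = 1.52 days.

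**Step 3: an illustration for ventilation.** Assume 10 deaths on IVIG and 18 on SMT, all ventilated from Day 1 and dying on Day 10. Half the survivors are never ventilated and the rest are spread evenly over 4 to 28 days (mean 16), so the survivor mean is 8.

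- f = 0: (10×29 + 40×8)/50 = 12.20 against (18×29 + 32×8)/50 = 15.56. Difference −3.36, pooled SD 12.43, SE 12.43 × √(2/50) = 2.49.
- f = 50%: (5×29 + 5×10 + 320)/50 = 10.30 against (9×29 + 9×10 + 256)/50 = 12.14. Difference −1.84, SE 2.18.
- f = 100%: (100 + 320)/50 = 8.40 against (180 + 256)/50 = 8.72. Difference −0.32, SE 1.64.

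The falls of 1.52 and 3.04 match Step 2. The ratios of difference to SE are −1.35, −0.84 and −0.19. None is significant, so what this shows is an effect on the estimate.

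**Step 4: t or f differs between arms.** The Step 2 formula no longer holds, and equal deaths do not protect the comparison. With 10 deaths per arm, on Day 6 in one and Day 16 in the other, and f = 100%, the means fall by 10×23/50 = 4.6 and 10×13/50 = 2.6 days, a shift of 2.0 at D = 0. As an extreme bound, take 15 deaths per arm on Day 10, with stop dates entered for all in one arm and none in the other. That gives 15×19/50 = 5.7 days.

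**The case against.** The best defence is that the condition is deliberate. Death in the ICU or in hospital is defined by place, but ventilation and oxygen can end before an in-hospital death, so some flag is needed to tell the two cases apart. An empty stop date is a reasonable flag. The rule for what to enter at death would normally sit in an eCRF completion guide, which is not among these documents. The SAP also lists all ventilation and oxygen data, so odd entries would be visible. These are two secondary endpoints in an open-label pilot with no multiplicity adjustment.

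Much of this stands. Some condition is needed, the frequency of the problem is unknown, and the weight is limited. What does not follow is that the SAP can stay silent. The flag works only under an entry convention that neither document states, and a listing shows the entries without giving a rule for handling them. The provision for support still ongoing at study completion does not alter a recorded stop date.

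Three stronger readings are tempting and are not supported.

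- A reader might infer a breach of SAP 4.4, under which "missing data for binary and selected continuous efficacy endpoints will be imputed using a most conservative/worst case approach". That sentence covers missing data, applies to selected endpoints and leaves the details to Section 6. A recorded stop date is not missing, so nothing in 4.4 is contradicted.
- A reader might infer that the sign of the treatment difference would reverse. That can be constructed: with 20% against 40% mortality, deaths on Day 10 and survivors averaging 14 days, the difference goes from −3.0 to +0.8 when every death has a stop date entered. It needs long support in survivors and entry at all deaths, and the documents give no ground for either.
- A reader might infer that every in-hospital death should be carried to Day 29. The plan does not say so, and a subject who came off support earlier can properly keep the recorded duration.

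**Conclusion.** The point holds as a gap in the derivation rule. As written, a subject on support from Day 1 who dies on support on Day 4, 10 or 20 scores either 29 days or 4, 10 or 20 days, depending only on whether the stop-date field was filled in. Neither document closes the gap.

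That much follows from the text. The size at trial level does not: D, f, t and survivors' days are all assumptions, and the entry convention cannot be seen here. Under a common t and f, a mortality-driven difference shrinks by f × D × (29 − t)/50. If either differs between arms, a shift can arise even with equal deaths. The consequence is confined to the estimates for ventilation days and oxygen days. No change of sign or of significance is claimed, and the primary Day 29 mortality analysis is not affected. It should be fixed because the remedy is cheap and removes a dependence on data-entry habit.

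**What to change.** In SAP 6.2, *Duration of mechanical ventilation*, replace the sentence on deaths with:

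*Subjects who died while on mechanical ventilation (stop date missing, or stop date equal to the date of death) will be assigned as on mechanical ventilation from the day of death to Day 29. Subjects whose recorded stop date is before the date of death keep their recorded duration. Subjects never placed on mechanical ventilation score zero days, including those who die.*

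Make the same change for oxygen in *Duration of any oxygen use*.

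Two details matter. Zero is tied to never having been on support, not to a missing start date, so that a ventilated subject with an incomplete record does not get the best possible score. The rule uses dates only, because the documents do not show that a time of death is collected.

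Cost: one sentence becomes three in each of two subsections, with a small programming change. The stop dates are already recorded, and the planned survival analysis already needs the date of death. The downside is that a subject who came off support on the day of death is scored as on support to Day 29. That should be rare, and it is in line with the ICU and hospital rules.

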#### **7.5 Other Safety Measures**

Data for COVID-19 clinical features will be listed and tabulated by treatment group.

Data for hospital interventions will be listed and summarized by presenting frequency counts and percentages for each category. The duration (number of days) of extracorporeal support and inotropes/vasopressors administration will be calculated based on the start/stop dates recorded on the eCRF and summarized descriptively. Subjects who were never on extracorporeal support or inotropes/vasopressors will be included in the descriptive summary with a value of zero days of duration.

Body weight assessments will be summarized by presenting descriptive statistics of raw data and change from baseline values at each time point by treatment group.

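### SAP 6.2 gives two conflicting values for ventilation days to a subject who dies in hospital without being ventilated, and one of them is the best possible score

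*SAP*

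**What the plan says.** SAP 6.2, Duration of mechanical ventilation, derives the number of days from start and stop dates on the eCRF. "Number of days on mechanical ventilation will be compared between treatment groups using an ANOVA model", with LS means, a confidence interval for the difference and a p-value. Two special rules follow in the same paragraph:

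- **Death rule.** "Subjects who died during the hospitalization without a stop date of mechanical ventilation recorded on the eCRF will be assigned as being on mechanical ventilation". The assignment covers whatever time is left until Day 29. The text asks for neither a start date nor ventilation at the time of death.
- **Zero rule.** "Subjects who are never placed on mechanical ventilation through Day 29 will be included in the analysis with a value of zero days". It makes no exception for subjects who died.

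The ICU rule in SAP 6.2 is built differently: "Subjects who died while in the ICU will be assigned as in the ICU for the number of days remaining from the day of death". The count ends at Day 29. It depends on where the subject was at death, and the hospital-days rule works the same way. The oxygen rules repeat the ventilation pair, including "Subjects who never received supplemental oxygen through Day 29 will be included in the analysis with a value of zero days of oxygen use".

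SAP 7.5 covers extracorporeal support and inotropes/vasopressors. Their durations "will be calculated based on the start/stop dates recorded on the eCRF and summarized descriptively". The only special rule is "Subjects who were never on extracorporeal support or inotropes/vasopressors will be included in the descriptive summary with a value of zero days of duration"; death is not mentioned.

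SAP 4.4 announces a worst-case approach for selected continuous efficacy endpoints, leaves the details to Section 6, and plans no imputation of this kind for safety analyses.

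**The concern.** Inclusion criterion 3b (Protocol 5.1) admits subjects on supplemental oxygen alone, so a subject can enrol, never be ventilated, and die in hospital. That subject has no ventilation stop date and was never ventilated, so both rules apply as written and give values at opposite ends of the scale. Two programmers could follow the SAP faithfully and disagree. Double programming (SAP 4.1) may expose the mismatch, but the SAP gives no basis for resolving it. In an open-label trial the choice could then be made with the arms known.

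Resolving it in favour of the zero rule leaves a second problem. An unventilated death would score the same as a survivor who never needed a ventilator, while a death on the ventilator is carried to Day 29. At stake is the value, and possibly the significance, of one tested secondary comparison.

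**Working it through.** The plan states no effect size, SD or event rate for this endpoint, and SAP 9 gives no sample size calculation, so there is no figure to reproduce. The check applies the two rules literally.

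**Value per subject.** SAP 4.6 counts duration as end minus start plus 1. Taking the days remaining from the day of death d, the death rule gives 29 − d + 1 = 30 − d days; the zero rule gives 0. Because the subject has no start date, the starting day is itself undefined. Counting from Day 1 would give 29.

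**Shift in an arm mean.** About 100 subjects at 1:1 is about 50 per arm. For k such deaths on Day d (both assumed), the shift between the two readings is k(30 − d)/50:

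| Death on Day | Days: death rule / zero rule | k = 1 | k = 2 | k = 3 |
|---|---|---|---|---|
| 5 | 25 / 0 | 0.5 | 1.0 | 1.5 |
| 10 | 20 / 0 | 0.4 | 0.8 | 1.2 |
| 20 | 10 / 0 | 0.2 | 0.4 | 0.6 |

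Counting from Day 1, each death would move the mean by 29/50 = 0.58 days.

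**Direction of the comparison.** Assume mortality of 30% (IVIG) and 40% (SMT), survivors averaging 8 ventilation days, ventilated deaths counted as 29, and unventilated deaths on Day 12 (18 days or 0). With q the share of deaths never ventilated, an arm mean is (1 − m) × 8 + m × [(1 − q) × 29 + q × v], where m is mortality and v is 18 or 0.

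| q in IVIG / SMT | IVIG − SMT, death rule | IVIG − SMT, zero rule |
|---|---|---|
| 10% / 10% | −1.99 | −1.81 |
| 30% / 30% | −1.77 | −1.23 |
| 50% / 50% | −1.55 | −0.65 |
| 70% / 70% | −1.33 | −0.07 |
| 10% / 50% | −0.23 | +2.83 |

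With equal shares the zero-rule difference is −0.1 × (21 − 29q), which stays negative until q exceeds 21/29 = 72%. With 10% in the IVIG arm, its mean is 5.6 + 0.3 × 26.1 = 13.43. The SMT mean, 4.8 + 11.6(1 − q), falls below that once q exceeds about 26%.

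**Effect on the test.** A simulation of 4,000 trials with 50 per arm used a two-sample t-test, equivalent to the two-group ANOVA. It assumed mortality of 25% against 45%, deaths uniform over Days 3 to 26, and ventilated deaths at 29 days. Forty percent of survivors were never ventilated, and the rest had 3 to 28 days.

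| q, both arms | p < 0.05, death rule | p < 0.05, zero rule | Readings disagree on significance | Readings disagree on sign |
|---|---|---|---|---|
| 10% | 36% | 30% | 9% | 4% |
| 30% | 27% | 14% | 14% | 11% |
| 50% | 22% | 7% | 17% | 23% |

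The sign disagreements arise by chance in single trials, since the underlying shares are equal.

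For scale, at q = 30% under the zero rule these inputs give variances of 135.4 (IVIG) and 159.7 (SMT), so the standard error of the difference is √((135.4 + 159.7)/50) ≈ 2.4 days. A shift of 0.2 to 1.5 days is less than one standard error.

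**SAP 7.5.** Assume mortality of 30% and 40%, and survivors with 6 vasopressor days. If deaths have 3 observed days, IVIG − SMT is (0.7 × 6 + 0.3 × 3) − (0.6 × 6 + 0.4 × 3) = 5.1 − 4.8 = +0.3, so the arm with more deaths shows less support. Counting deaths as 29 days gives −2.3. If deaths have 8 observed days, the observed difference is −0.2 and there is no reversal.

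**The case against.** The strongest reply is that the conflict is not intended. A rule about a missing stop date presupposes that ventilation started, and the zero rule names the never-ventilated subject specifically. This is probably what the authors meant, but the text does not say so. It also settles only the ambiguity: the unventilated death still takes the lowest possible value on a tested endpoint.

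Several stronger inferences are tempting, and the documents do not support them:

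- **That such deaths are expected.** They are possible. No document gives a count, and exclusion 7 (no limitation of therapeutic effort at entry) may keep them few.
- **That every other duration endpoint carries deaths to Day 29.** The ICU and hospital rules carry only the subject's state at death, and the oxygen rules share the ventilation wording. Never-oxygen deaths are unlikely given inclusion 3b.
- **That the section already contains the remedy.** The paragraph with the death rule also holds the zero rule, and neither is placed above the other.
- **That ventilation days will run against mortality.** With equal shares of never-ventilated deaths at 10% to 70%, the expected sign did not change.
- **That SAP 7.5 biases a test.** ECMO and vasopressor days are not listed endpoints, SAP 7 plans no formal testing for safety, and observed exposure is a legitimate descriptive quantity.

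It is also fair that carrying unventilated deaths forward makes the endpoint partly a mortality measure, when mortality is already primary and death is already the worst ordinal category. That argues for reporting observed days as well, not for leaving two rules in place.

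**Conclusion.** The point holds for SAP 6.2. A never-ventilated in-hospital death has two literal values with no stated precedence. One of them has no defined starting day; the other is the best score available. The consequence is confined to one secondary endpoint in a pilot without multiplicity control. One to three such deaths in an arm of 50 would move its mean by about 0.2 to 1.5 days, assuming deaths between Day 5 and Day 20 and counting from the day of death. Under the simulation inputs, the choice of reading changed significance in 9% to 17% of trials.

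A reversal of the expected sign needs the never-ventilated share of deaths to differ markedly between arms (under the inputs above, 10% against more than about 26%) or a common share above 72%. All mortality, timing and duration inputs are assumptions. For SAP 7.5 the conclusion is only that a short course ended by death can read as less support.

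**What to change.** Before database lock, amend SAP 6.2 to state one rule for ventilation days covering every death through Day 29: never ventilated, ventilated with a recorded stop date, and after discharge. The last two need naming because the present death rule reaches neither. Either of these would serve:

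- carry each death from the day of death to Day 29, added to any ventilation days observed before it; or
- use ventilator-free days through Day 29 with death set to 0. A rank-based comparison would suit this, and Protocol 9.1 already allows the Wilcoxon test for non-normal variables.

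Limit the zero-day rule to never-ventilated subjects who did not die by Day 29. State how unknown vital status is handled; SAP 6.1 treats it as death for the primary analysis. Because the endpoint becomes partly a mortality measure, also report observed ventilation days separately for survivors and deaths.

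In SAP 7.5, present ECMO and vasopressor days split by survival status. No imputation is needed.

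The cost is SAP wording, one derivation rule and a table split. No new data are required.
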